- 1.3. Identify the barriers and facilitators for recruiting and retaining peer counselors.
- 1.4. Create a culturally appropriate training curriculum for BEST4Baby to prepare peer counselors for their roles.

Primary Aim 2: Evaluate the usability and feasibility of the BEST4Baby's mHealth application to support a community based program utilizing peer counselors to provide breastfeeding support to Indian mothers. Objectives for this aim are:

- 2.1. Develop the BEST4Baby's mHealth application prototype to support peer counselors.
- 2.2. Assess the effect size of the BEST4Baby program with 24 peer counselors who each will support 5 breastfeeding mothers (total of 120) from study clusters who deliver their babies during a 9-month pilot by comparing breastfeeding practices among 120 mothers who reside in adjacent communities and have not been provided breastfeeding counseling.

The primary outcome of this research is hypothesized to be an increase in relevant training and capabilities for supporting peer counselors using the BEST4Baby program. A secondary outcome is hypothesized to be an increase in EBF rates at 6 months postpartum among mothers coached by peer counselors. These mothers will learn when to initiate healthful complementary foods and be more likely than the comparison group to express a willingness to continue breastfeeding for an appropriate time when intent is measured prior to the close of this 2-year project. The outcomes for the proposed research are significant due to their focus on sustainable strategies for EBF, a critical infant health intervention. The BEST4Baby methodology is innovative as it involves development of low-cost technology suitable for cell phones and tablets and appropriate for use during training and to support peer counselors as well as mothers. Our highly qualified, inter-disciplinary, international research team has the skills and experience necessary to successfully complete all proposed activities. The team has training experience and expertise, knowledge of lactation practices among Indian women, capabilities in maternal/child health research including community-based participatory research (CBPR), skills in quantitative and qualitative methodology and rich background in leading-edge information and communication technologies.

Significance

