Breastfeeding, a natural and safe means of feeding infants, provides nutritional, immunologic, psychological and economic benefits with recognized and unquestionable advantages. Human milk is a complex —species-specific biological fluid, adapted throughout human existence to perfectly satisfy the nutritional and immunological needs of the child⁵. For many years BF has been known to be an important intervention in developing countries to reduce mortality from infectious diseases and malnutrition³. However, only 39% of all infants worldwide receive EBF, even when the assessment is made in children less than four months of age^{18,19}. Factors such as maternal age >35 years, nulliparity, low birth weight, resuscitation, and delivery by caesarean section contribute to the lack of EBF in settings found in India, where infant and young child feeding practices are not optimal. Studies in India show that EBF drops rapidly from the first month to the sixth month by which time only 20% of children are still being breastfed²⁰

Most national and international organizations that monitor health outcomes strongly recommend breastfeeding. Since May 2002, the World Health Organization and UNICEF have jointly developed and supported the Global Strategy for Infant and Young Child Feeding to revitalize global attention on the impact of feeding practices for improving child survival, growth and development. In 2011, the Breast Feeding Promotion Network of India initiated a plan to enhance the practice of BF in the country. The action plan suggested the opening of resource centers, counseling services and communication campaigns²⁰. In August 2016, India launched a nationwide program, Mother's Absolute Affection (MAA), to bring undiluted focus on the promotion of BF and to ensure that mothers receive counseling and support by family members and at health facilities. The BEST4Baby program will build upon both these initiatives while focusing on the implementation and sustainability of utilizing peer counselors for breastfeeding support using an mHealth app.

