Multimedia content. Multimedia content will be developed based on Social Cognitive Theory (SCT)³⁹, Theory of Planned Behavior (TPB)⁴⁰ and social marketing (e.g., health branding) approaches^{41,42} for use by peer counselors for breastfeed during the home visits. Message development will follow active audience engagement methods and be suitable for use by peer counselors to provide information to mothers during antepartum home visits.

Communication features. Timely communication of information based around post-partum time sequence and baby's milestones will be developed to assist the peer counselors in promoting optimal breastfeeding practices. Counselors may be reminded of the need for follow-up via text reminders and communications may support the home visits by providing helpful hints that are introduced in a timely manner. For example, the peer counselors could be prompted to discuss the topic of EBF at 28 weeks GA and at a second visit 1-2 weeks before anticipated delivery.

Months 15-23

For Specific Aim 2, we will pilot test the BEST4Baby program in a real-life setting within the 6 clusters of the larger Global Network research area located in Belagavi District (Karnataka, India). The pilot study will evaluate training for 24 peer counselors recruited from study areas and providing consent; and the study will assess use of the BEST4Baby program to support counselors as well as mothers recruited and consented by research staff to receive peer counseling. Each peer counselor will counsel 5 mothers to achieve a sample adequate to establish an effect size.

Peer Counselors for Breastfeeding Support. The 24 peer counselors will evaluate the usability and acceptability of the mHealth app for the training and support provided. We will perform pre- and post-tests to identify knowledge acquired as a result of peer counselor training and administer a post-training survey on the usability and acceptability of the BEST4Baby program. As peer counselors are being trained, they will receive an ID badge²⁸, the BEST4Baby mobile application and branded BEST4Baby mobile device to support the training.

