Comparison Cohort. To enable effect and sample size calculations, an appropriate comparison cohort will be used. We will obtain baseline and six-month post-partum data from a control group of 120 women delivering in facilities and living a suitable distance from study clusters to avoid contamination. A simple survey will be developed and administered by research staff to collect data comparable to that collected from mothers counseled (e.g., current BF practices and future intentions for continuation of breastfeeding). Women in this comparison cohort will provide informed consent and be provided with a small gift (e.g., a branded carrying bag) to show appreciation for their participation.

Month 24

Data Analysis. For survey, application utilization, and subject data associated with Specific Aim 2, we will conduct bivariate analyses (crosstabs, Chi-square procedures) to examine demographics and other measured variables potentially related to breastfeeding. Changes from baseline to follow-up in breastfeeding and other study outcomes and potential moderating variables (e.g., lifestyle changes due to childbirth and behaviors) will be examined.

We will also document engagement in and use of the BEST4Baby program by both the peer counselors and new mothers. The BEST4Baby program will collect usage data, (e.g., utilization, approximate time spent in use of application during home visits) in the follow-up interviews. These combined process measures will be calculated as a _dosage index' and used as a covariate in subsequent analyses. The dosage index will both 1) document process and 2) serve as an independent variable for multivariate modeling. Dosage measures will include time/counts of activity, intensity, engagement, and satisfaction, and will serve to document the feasibility of the BEST4Baby approach to train the peer counselors as well as to support new mothers to initiate and continue breastfeeding.

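### The Month 24 analysis names no estimator or interval for the counselled v comparison effect size (Objective 2.2) and makes no allowance for clustering, so standard independence-based tools would overstate its precision

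*Combined protocol and SAP*

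**What the plan says.** Objective 2.2 under Primary Aim 2 is to assess the programme's effect size in 120 counselled mothers by "comparing breastfeeding practices among 120 mothers who reside in adjacent communities and have not been provided breastfeeding counseling". The outcome at issue is secondary: "A secondary outcome is hypothesized to be an increase in EBF rates at 6 months postpartum among mothers coached by peer counselors". The Months 15-23 section ties the workload to this purpose: "Each peer counselor will counsel 5 mothers to achieve a sample adequate to establish an effect size". The Comparison Cohort paragraph says "To enable effect and sample size calculations, an appropriate comparison cohort will be used", and the Conclusion of the analysis section says the findings will support an application for a fully powered trial.

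Section I.a (Human Subjects Involvement, Characteristics, and Design) takes four counsellors from each of six clusters, with 5 mothers each. It also says that assignment is not random and depends on where a mother lives.

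The comparison mothers are described in three ways: as living in adjacent communities (Objective 2.2 and section I.a), as "women delivering in facilities and living a suitable distance from study clusters to avoid contamination" (Comparison Cohort), and as coming from non-participating clusters (section I.a). The number of comparison clusters is not given. Their total is 120 in Objective 2.2, in Comparison Cohort and in the section I.a account of the subject population, but the section I.a paragraph on assignment prints it as 12, in parentheses.

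For analysis, Month 24 says "we will conduct bivariate analyses (crosstabs, Chi-square procedures) to examine demographics and other measured variables potentially related to breastfeeding". It adds an examination of change from baseline, a dosage index that will "serve as an independent variable for multivariate modeling", and exact logistic regression of breastfeeding outcomes on dosage. It mentions no ICC, design effect, mixed model, GEE or robust error.

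**The concern.** Mothers in the same cluster share facilities, health workers, customs and, in the counselled group, counsellors. Their feeding outcomes are therefore likely to be correlated. Each cluster lies wholly in one group, so between-cluster variation enters the group difference in full. An analysis that counts 240 independent mothers treats that variation as if it were absent.

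What is at stake is the stated product of this part of the pilot: an effect size, with its uncertainty, to be used in planning a larger trial. It is not the only planning input, because section I.a also proposes to judge improvement against published Karnataka figures. An interval that is too narrow would still give that planning unwarranted confidence.

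**Working it through.** **Inputs from the documents.** 6 clusters x 4 counsellors = 24 counsellors; 24 x 5 mothers = 120, which reproduces the plan's figure. This is a workload count: the documents give no alpha, power, target difference or ICC, so there is no precision calculation to reproduce. 120 / 6 = 20 mothers per cluster, if counsellors serve their own cluster. Comparison group: 120.

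**Assumptions.** ICC 0.01, 0.02, 0.05, 0.10. Comparison mothers from 6 clusters of 20 (alternatives below).

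**Formulas.** Design effect DE = 1 + (m - 1) x ICC, with m = 20. Effective size = 120 / DE. SE multiplier for the contrast = square root of the mean of the two groups' DEs. Interval multiplier = SE multiplier x t(10 df) / z = SE multiplier x 2.228 / 1.960 = SE multiplier x 1.137.

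| ICC | DE | Effective n of 120 | SE multiplier | Interval multiplier | Coverage of naive 95% interval |
|---|---|---|---|---|---|
| 0.01 | 1.19 | 101 | 1.09 | 1.24 | 92% |
| 0.02 | 1.38 | 87 | 1.17 | 1.34 | 90% |
| 0.05 | 1.95 | 62 | 1.40 | 1.59 | 83% |
| 0.10 | 2.90 | 41 | 1.70 | 1.94 | 74% |

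Coverage is from a beta-binomial simulation (60,000 runs, true rates 40% v 20%, exchangeable clusters, no confounding). A cluster-level t interval on 10 df covered about 95% at every ICC.

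**Example.** The Significance section gives a six-month background figure ("by which time only 20% of children are still being breastfed"), used here only to illustrate; 40% in the counselled group is assumed. Naive SE = sqrt(0.2 x 0.8/120 + 0.4 x 0.6/120) = 0.0577. The naive 95% interval for the 20-point difference is 20 +/- 1.96 x 5.77 = 8.7 to 31.3 points. Multiplying the SE by sqrt(DE) and using t = 2.228 gives 6.0 to 34.0, 4.9 to 35.1, 2.0 to 38.0 and -1.9 to 41.9 points at the four ICCs.

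**Sensitivity, in the same ICC order.**
- Naive coverage by comparison layout: mothers scattered (no clustering) 93/92/88/81%; 12 clusters of 10, 93/91/86/78%; 2 clusters of 60, 91/86/75/63%.
- If only 12 mothers per cluster have six-month data (assumed), DE = 1 + 11 x ICC and the SE multiplier falls to 1.05/1.10/1.24/1.45.
- Counsellor-level correlation alone (m = 5, counselled group only): DE = 1 + 4 x ICC = 1.04/1.08/1.20/1.40 and contrast SE multiplier 1.01/1.02/1.05/1.10. Cluster is the level that matters.

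**Is a routine correction safe for the dosage models?** With only 6 counselled clusters, an uncorrected cluster sandwich in an ordinary logistic model rejected about 12-16% of the time at a nominal 5% in simulation. The unadjusted test rejected about 4-10%. The sandwich with the G/(G - 1) = 6/5 factor and t on 5 df rejected about 4-6%. The uncorrected form is worse than no adjustment.

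**The case against.** The strongest reply is that this is exploratory, non-randomised work on a secondary outcome, with no hypothesis test or precision target for the contrast. Confounding by area and incomplete six-month follow-up may threaten the effect size more directly than a narrow interval does. That stands, and it limits the weight of the point. It does not remove it, because an effect size for planning is what the comparison cohort is for.

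The chi-square sentence covers survey and subject data for Aim 2 and can be read to include group. Even so, a chi-square test gives neither an effect size nor an interval, and it still assumes independent mothers.

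The size is also assumed throughout. At ICC 0.01-0.02 the SE is only 9-17% too small.

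A reader might infer more than the documents support:
- That the contrast will be analysed naively. The plan does not say how it will be analysed; the loss of precision is conditional on that choice.
- That the effect estimate is biased or the next trial will be undersized. Ignoring clustering does neither by itself.
- That each counsellor serves only her own cluster. The text implies this (four per cluster, ideally living near their mothers) but does not state it. The figure of 20 per cluster depends on it.
- That only 12 comparison mothers are planned. Three other places say 120, so 12 is probably a misprint, but the passages must be reconciled.

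**Conclusion.** The point holds and should be fixed before the comparison cohort is recruited. It is certain from the text that no listed analysis allows for clustering and that none is stated to estimate the Objective 2.2 contrast with an interval. The consequence is conditional: with independence-based tools, precision is overstated for any positive ICC.

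The loss runs from modest to serious over the assumed range. It rests on assumed ICCs, an assumed comparison layout and about 20 mothers per cluster. The dosage models are a lesser matter. No inflation figure is offered for them, because a Wald-type approximation does not describe the planned exact model.

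**What to change.** 1. **Group contrast.** In the Month 24 analysis, name the counselled v comparison difference as an estimate. Obtain it from cluster-level proportions with a t interval on cluster degrees of freedom (10 with 6 v 6 clusters), or by GEE or a mixed model with a small-sample correction. Do not enter cluster as a fixed effect or stratum here: group does not vary within cluster, so its effect could not be estimated.
2. **Dosage models among counselled mothers.** Use exact logistic regression stratified by cluster, or cluster-robust errors only with a small-sample correction such as the G/(G - 1) factor with t on 5 df. State whether comparison mothers enter these models.
3. **Data and sampling.** Record the cluster code for all 240 mothers, and state whether counsellors work only within their own cluster. Preferably draw comparison mothers from several clusters named before recruitment. With 6 comparison clusters the median half-width of the cluster-level 95% interval in simulation is 14/15/17/21 points at the four ICCs; with 2 it is 17/18/23/29. Reconcile the two figures for the comparison group.
4. **Reporting.** Give the ICC with its interval, and plan the next trial from the clustered interval and a range of ICCs. Say beside the effect size that cluster adjustment does not remove confounding from non-random assignment.

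**Cost.** Mostly analysis wording, plus a small constraint on sampling. Cluster is already largely recoverable for counselled mothers through counsellor identification numbers, addresses and the retained cluster of residence; the code must be made firm for comparison mothers, who have no counsellor. The price is wider intervals and an imprecise ICC: with 12 clusters of 20, the central 95% of simulated estimates runs from -0.02 to 0.15 when the true value is 0.05.

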Barriers to early initiation, exclusive BF for 6 months, introduction healthful complementary feeding at the appropriate time, and continued BF include demographics (e.g., maternal age, parity, educational status, family size/type), socio-cultural variables (e.g., attitudes, family support, cultural perceptions, customs, etc.), and system factors (e.g., place and type of birth attendant, availability of counselors)^{8,9}. Achieving optimal infant feeding practices requires a multi-pronged approach that will not only involve health care providers and policy makers but will also enlist community participation and support^{10,11}.

One strategy for increasing BF initiation and duration is developing and sustaining community-based programs which utilize peer counselors for breastfeeding support. Such programs have demonstrated effectiveness in both developed and developing countries^{6,8,12-14} including India¹⁵⁻¹⁷. The proposed research will investigate the behavioral, structural, and systemic factors that influence decisions of mothers in India related to exclusive BF and BF duration; findings will be used to develop a comprehensive program using mobile health (mHealth) technology to support peer counselors in their work with lactating mothers. The mHealth application (app) will be integrated into the training of peer counselors, provide multimedia job aids for the counselors' sessions with mothers, and provide an integrated communications network among counselors, local health centers and BF mothers. The goal of the research is to design and develop a comprehensive, culturally-relevant, community-based, peer counselor training program with an mHealth support app called Breastfeeding Education Support Tool for Baby (BEST4Baby) program.

Specific aims of the research are:

Primary Aim 1: Determine the conditions necessary to develop a program to educate and support peer counselors. Four objectives for this aim are:

- 1.1. Determine the knowledge, attitudes, beliefs, behaviors, motivations and barriers around the initiation and continuation of EBF to 6 months, introduction of healthy complementary foods at the appropriate time, and continued breastfeeding from the perspective of BF mothers and their support networks (i.e., husband, mother-in-law, etc.).
- 1.2. Assess the acceptability and feasibility of the peer counselor model for improving EBF rates and other BF practices.

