We plan to: (1) apply exact logistic regression models to determine if the level of participation in BEST4Baby is associated with an increase in optimal breastfeeding practices, and (2) test mechanisms underlying behavioral outcomes hypothesized in the conceptual model leveraging social cognitive theory, theory of planned behavior, and social marketing. Exact logistic regression models will examine the effect of BEST4Baby dosage, using the dosage index based on pilot test usage and self-report data as independent variables, on 6-month continued breastfeeding. We will calculate odds of exclusive breastfeeding, mixed feeding and use of milk substitutes at follow-up as a function of BEST4Baby dosage based on utilization and process data.

Conclusion: We anticipate that the BEST4Baby program will substantially increase the capacity of the JNMC Women's and Children's Health Research Unit to incorporate mHealth technologies into future use and health care delivery. We plan to utilize findings generated by analysis of BEST4Baby data to develop an application for a fully powered control trial to assess the separate and combined impact of a peer counselor program and mobile applications to support such a program. Cost considerations and greater attention to sustainability will likewise be addressed in that application.

I. Risks to Human Subjects

a. Human Subjects Involvement, Characteristics, and Design

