Subjects that take the BEST4Baby training will take pre- and post-tests to assess if training increased breastfeeding knowledge; these women will also be asked to provide feedback relative to the acceptability of mHealth technologies and tools developed during the BEST4Baby program and to share perceptions about the perceived feasibility of continuing their use during an extended period of service as a counselor. Mothers will be recruited by research staff and asked to consent to being counseled during home visits and to providing data needed for purposes of BEST4Baby. Research staff will obtain feedback and ask questions to generate information about breastfeeding (e.g., when it was initiated, if exclusive breastfeeding occurred, how long any type of breastfeeding was maintained, and intent to continue breastfeeding beyond the close of BEST4Baby). A group of mothers not receiving peer counseling will also consent and serve as a comparative group to assess if breastfeeding practices are better among peer-counselled mothers compared to mothers not having peer counseling.

It is planned that data generated by the BEST4Baby formative research will be utilized for the design of a clinical trial that can generate definitive findings relative to the effectiveness of mobile technologies to promote optimal breastfeeding and to increase sustainability of a peer counselor model for delivery of breastfeeding support.

Describe the characteristics of the subject population, including their anticipated number, age range, and health status, if relevant. Focus groups will have 8-10 participants and all participants will consent before initiation of focus group discussions. At least two focus groups will be held for each target group described below, except that there will be at least one Target Group A focus group in each of the six clusters selected from among the clusters located within the larger JN Medical College Global Network study area for participation in BEST4Baby. Characteristics of focus group target groups follow.

Target Group A: This group will be comprised of mothers who have breastfed at least one child in the past three years. Other inclusion criteria include: 18 years of age, and willing to provide informed consent. To the extent feasible, mothers representing the diversity that exists in the cluster of residence will be encouraged to participate. A Target Group A focus group will be held in each of the 6 clusters participating in BEST4Baby.

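### Objective 2.2 compares groups formed by residence, but no counselled-versus-comparison estimate adjusted for confounders is specified

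*Combined protocol and SAP*

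**What the plan says.** Objective 2.2 sets out to assess the effect size of the programme by comparing 120 counselled mothers with 120 uncounselled mothers. The Comparison Cohort paragraph gives the purpose: "To enable effect and sample size calculations, an appropriate comparison cohort will be used". It describes the cohort as a "control group of 120 women delivering in facilities and living a suitable distance from study clusters to avoid contamination". Section I.a says that the comparison mothers are there "to assess if breastfeeding practices are better among peer-counselled mothers compared to mothers not having peer counseling". Its paragraph on assignment says that allocation is not random: residence in a study cluster decides who can be counselled.

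For the analysis, the Month 24 text says "we will conduct bivariate analyses (crosstabs, Chi-square procedures) to examine demographics and other measured variables potentially related to breastfeeding". It adds that changes from baseline and potential moderators will be examined. A dosage index is to serve as a covariate and as an independent variable in multivariate modelling. "Exact logistic regression models will examine the effect of BEST4Baby dosage" on continued breastfeeding at six months, and mechanisms from the conceptual model will be tested. The Conclusion says that the findings will feed an application for a "fully powered control trial to assess the separate and combined impact of a peer counselor program and mobile applications".

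The Background lists "demographics (e.g., maternal age, parity, educational status, family size/type" among the barriers to good feeding practice. The Significance section adds maternal age over 35 and nulliparity as contributors to lack of EBF. Section II (Sources of Materials) includes socio-demographic survey data from mothers.

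**The concern.** Women in different communities may differ in age, parity, education or family type. The protocol itself ties these to feeding practice. A raw difference in EBF between the two groups then mixes the effect of counselling with the effect of who lives where. The plan names the likely confounders and intends to collect socio-demographic data, but it does not say that the group contrast will be adjusted.

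At stake is the number that the comparison cohort exists to supply. If the pilot's effect size is crude, any confounding in it passes into the planning of the next trial. A larger sample would not remove that error, and an ordinary confidence interval does not show it.

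**Working it through.** **1. The plan's own figure.** 6 clusters x 4 counsellors x 5 mothers = 120 counselled, which reproduces. The comparison number is 120 in Objective 2.2, in the Comparison Cohort paragraph and in the population paragraph of section I.a. The assignment paragraph prints 12, which looks clerical. No alpha, power, event rate or intracluster correlation (ICC) is given, so no other figure can be reproduced.

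**2. Each planned analysis, set against what Objective 2.2 needs** (study group as exposure, confounders adjusted):
- Crosstabs and chi-square: can compare the groups, but without adjustment.
- Changes from baseline and moderators: to be examined; no model, exposure or covariate list is given.
- Mechanism tests: address theory-based pathways, not the group difference.
- Multivariate and exact logistic models: the named exposure is the dosage index, built from app use, time, engagement and satisfaction. These arise after enrolment, and no value is stated for comparison mothers. The result is an association with dose, not the counselled-minus-comparison difference, and no confounder is named for these models.

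Matching, weighting and stratification of the two groups are not mentioned either. The only defined method left for the group contrast is a crude comparison.

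**3. Possible size of the shift (all inputs assumed).** For one binary covariate, bias in the risk difference = (difference in its prevalence between groups) x (difference in EBF by that covariate).
- 0.10 x 0.10 = 1 point
- 0.20 x 0.20 = 4 points
- 0.30 x 0.30 = 9 points

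The sign can be either way.

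**4. Sampling error for scale.** Assume 20% EBF in the comparison group and 40% in the counselled group, 120 each, all evaluable. The half-width of the 95% interval is 1.96 x sqrt(0.16/120 + 0.24/120) = 1.96 x 0.0577 = 11.3 points. With a common rate anywhere from 20% to 60% it is 10.1 to 12.7 points. The whole 1 to 9 point range therefore lies below the half-width.

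**5. Effect of allowing for clusters.** Take 20 mothers per cluster, six clusters per group (assumed for the comparison side) and ICC 0.01 to 0.05. The design effect is 1 + 19 x ICC = 1.19 to 1.95. With t on 10 degrees of freedom (2.228), the half-width is 2.228 x 0.0577 x sqrt(1.19) = 14.0 points, up to 2.228 x 0.0577 x sqrt(1.95) = 18.0 points. Simulation of the adjusted estimate under the same rates, with one covariate that changes EBF by 20 points, gave 13.7 to 17.4 points.

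**6. Is the widening due to the adjustment?** In simulation with cluster-corrected standard errors throughout, the half-width without and with covariate adjustment was 13.6 v 13.8 points at ICC 0.01 and 17.2 v 17.3 at ICC 0.05. Almost all of the widening comes from the cluster correction.

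**The case against.** The best defence is that this is a declared exploratory pilot. Non-random assignment is disclosed and explained, section I.a says that there is no rigid sampling plan, EBF is a secondary outcome, and a fully powered trial is to follow. The plan also goes beyond crude tests: it mentions multivariate modelling and uses dosage as a covariate, which implies models with other terms. Any plausible confounding may be smaller than the sampling error.

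Most of this stands, and it limits the importance of the point. It does not fill the gap. An exploratory aim excuses low precision. It does not explain why the quantity that the cohort was set up to provide is left undefined when the means to adjust it are largely at hand.

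A reader might infer more than the documents support:
- That the non-randomised design is itself an error. It is disclosed and suits the stated purpose.
- That the effect will be overstated or the next trial underpowered. The direction of confounding is unknown, and that trial is to assess separate and combined components, so its size does not follow from this one contrast.
- That the cohort descriptions contradict each other. Adjacent communities and a suitable distance can both be true, because no distance is defined. Facility delivery may be description or an entry rule.
- That taking baseline data at the first counselling visits spoils the adjustment. Age, parity, education and family type are not altered by a counselling visit, and comparable data are planned for the comparison cohort.

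**Conclusion.** The point holds in a limited form. Models are planned, but none is defined with counselled versus comparison as the exposure and confounders adjusted. Followed as written, the Objective 2.2 effect size would be a crude difference between communities.

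The size and direction of the confounding cannot be derived from the documents. The 1 to 9 point range rests wholly on the assumed imbalance and association, and such a shift may be below sampling error. The importance is modest, but the correction is cheap and bears directly on the figure meant to inform the next trial.

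**What to change.** Prespecify the Objective 2.2 estimate as the counselled-minus-comparison risk difference in EBF at six months. Adjust it for a few covariates that the Background already names (maternal age, parity, education, family type), recorded the same way in both groups. Use cluster-robust standard errors with a correction for the small number of clusters, and report the result beside the crude difference.

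Keep the dosage model as a separate analysis within counselled mothers. Treat the state-survey rates cited in section I.a as context only, since comparison with them does not remove confounding. State residual confounding as a limitation, including willingness to be counselled: on the counselled side, "Mothers will be recruited by research staff and asked to consent to being counseled during home visits", while comparison mothers agree only to be interviewed.

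Minor wording: reconcile the adjacent location (Objective 2.2; section I.a, assignment) with the distance wording in the Comparison Cohort paragraph, say whether facility delivery is an entry rule, and correct 12 to 120.

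Cost: slightly more analysis, and naming parity and family type on the form, because section II does not itemise the socio-demographic data. The interval will be wider, with a half-width of about 14 to 17 points instead of 11 at an assumed ICC of 0.01 to 0.05. That comes from the cluster correction rather than the adjustment.
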